We will use multiple methods to recruit clients. We will do presentations at staff and client meetings and host lunches/ dinners at the research sites to introduce the project to clients and staff and answer any questions they may have about the project. Interested participants will be asked to provide study staff with their names and contact information. We will also accept provider referrals. Study staff will then initiate contact with interested clients via telephone or in person at each site to further explain the project and set up a face-to-face meeting at the study site to screen potential participants for eligibility, and for those eligible conduct the written consent process.

Once a client has been screened for eligibility into the study and provided informed consent, the study staff will schedule the initial baseline interview based on participants’ availability and preference. The baseline interview will last approximately 90-minutes and will be conducted by a trained research assistant (RA) in a private room at the study site in participants’ preferred language (English or Spanish). Randomization will occur after participants have completed the baseline interview on a 1-to1 ratio to intervention or usual care condition by a computer-generated random number program with treatment assignment kept in sealed, opaque envelopes. For participants randomized to the Peer GLB intervention, study staff will provide each participant a copy of the approval letter that the participant can take to their primary care physician for review and signature. Participants will be required to bring their doctor’s approval letter to the first Peer GLB group meeting in order to participate in the lifestyle intervention. The study staff, with assistance from the peer specialist at each study site, will help coordinate participants’ visits to their primary care physician to obtain this medical clearance. Failure to obtain this approval letter will preclude the individual from participating in the Peer GLB intervention. For participants randomized to the intervention group, baseline interviews will occur at most two weeks before the first group session. After the baseline interview is completed, the study staff will provide the participant the date and time of the first group session meeting.

Peer-Led Group Lifestyle Balance Intervention

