[name], study Principal Investigator, is a certified GLB group-facilitator having completed the 2- day facilitator training workshop provided by the DPSC and having facilitated GLB groups in previous studies. This training also provides ongoing implementation support through telephone conferences calls, on-line discussion board, GLB-listserv, GLB program directory, and Newsletters.

Description of Peer Specialists

Peer GLB will be facilitated by trained peer-specialists employed at the supportive housing agencies. According to SAMHSA, a peer specialist "is a person who uses his or her lived experiences of recovery from mental illness and/or addiction, plus skills learned in formal training, to deliver services in behavioral health [and other] settings to promote mind-body recovery and resiliency." The Peer Specialists will be employees hired by the supportive housing agency. They are individuals who are 18 and over, who have at least a high school education or GED equivalent, and who have completed prior training enabling them to become service providers. The qualifications of peer specialists hired at each study site include prior completion of extensive training in delivering services to populations with serious mental illness as well as certification, or in the process of receiving certification, for the delivery of peer specialist services per state regulations. These trainings to become a peer specialist include developing an understanding of the public mental health system, becoming integrated into the workforce, and intensive training in how to assist people with SMI in their recovery. As a result of these completed trainings, the peer specialists have expertise in 1) sharing their personal recovery experience to help others understand their experience of mental illness and treatment services, 2) assisting persons with SMI to identify

and overcome barriers to recovery and participation in services, and 3) assisting persons with SMI to develop skills that promote recovery, health, and wellness. Through the completion of this training and previous experience, peer specialists will have the ability to provide services either one-on-one or in groups. Each supportive housing agency will also provide peer specialists with its usual orientation and training that is required of all new employees prior to delivering services to clients.

Peer Specialist Intervention Training and Supervision

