Lastly, participants assigned to the intervention will be asked to complete one semi-structured qualitative interview that focuses on the participants' experiences with the group facilitator and explores specifically how intervention services were delivered from the participants' perspective. This semi-structured qualitative interview will be conducted after the transition phase of an intervention group has been completed. Participants who attended at least two intervention sessions will be asked to complete the interview and a total of 55 participants are expected to participate. The interviews last approximately 90 minutes and will be conducted in person by Drs. [name] (PI) & [name] (PD) and/or a trained research assistant at the study site. Examples of questions include: Is there anything that makes the healthy lifestyle peer specialist/facilitator unique from other provider staff that you have worked with? What are some of the peer specialist's/facilitator's best qualities? What kinds of things did your peer specialist/facilitator do to model or show you how to engage in a healthy lifestyle?

Criteria for Early Discontinuation

Early discontinuation from the study will be ascertained by the group facilitator in consultation with the participants' service providers (e.g., case managers) at the supportive housing agency. Participants who during the course of the project are in need of detoxification and are at acute risk of suicide or homicide will be referred for treatment and discontinued from the study. Moreover, participants that develop contraindications to participating in a weight loss program, such as receiving active cancer treatment (radiation/chemotherapy), develop liver failure, have a cardiovascular event (e.g., unstable angina, myocardial infarction) and become pregnant or are planning a pregnancy during the study period will be discontinued from the study.

4. Study Drugs or Devices: Not applicable.

5. Study Instruments

Structured Interviews: Baseline and 6, 12, and 18-month Follow-Up

The structured interview includes the collection of basic anthropometric measures and a simple physical activity measure by trained research staff:

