Project staff will then answer any questions, schedule a time to conduct the screening questionnaire, meet with the interested client in-person, read the screening eligibility information sheet, obtain verbal consent to complete the screening eligibility questionnaire, and complete the screening questionnaire for those who provide verbal consent. For those who are determined to be eligible, project staff will then administer the informed written consent process for participation in the effectiveness trial. Once clients have provided informed consent for the effectiveness trial, we will complete the baseline interview and carry out random assignment. For participants randomly assigned to the Peer GLB group, we will work with supportive housing agency staff to obtain the approval letter from the participants’ primary care doctor. Participants who have been consented will be given the date and time of the first group session and a reminder card of this first session. Project staff will also call participants one or two days before each groups session to remind them of their group sessions. Failure to submit the medical clearance letter by the first group session will preclude the person from participating in the Peer GLB intervention.

How will project be advertised/publicized?

As we have done in our previous research projects at community agencies, the research staff (PI, project director, and/ or research assistant) will present the project at different staff meetings. With the permission of program staff, we will also present the study at client meetings where events and new initiatives are discussed with clients. We will also host lunches/dinners at each study site to introduce the project to clients and staff. We will distribute a one-page description of the study to agency staff so that they can also present the study to interested clients (see attached: Project Description for Staff).

Compensation

Participants will be compensated for completing study assessments (e.g., structured interviews) not for attending intervention sessions. Participants will receive \$25 plus a round-trip transportation reimbursement (e.g., MetroCard in NY, two transit tokens in Philadelphia) for participating in each of the structured interviews at baseline, and 6, 12, and 18 months after baseline. The \$25 compensation will be given in cash at the end of the individual interviews.

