We will take several steps to minimize all of these risks. All participants randomly assigned to the Peer GLB intervention will be referred to a medical provider to determine whether it is safe for them to participate in the intervention prior to beginning Peer GLB. Only participants who obtain this medical clearance will be able to participate in the Peer GLB intervention. We will further minimize these risks through group sessions and individual counseling that will teach participants about: 1) the importance of properly engaging in moderate physical activity, warm-up and cool-down exercises, proper stretching and exercise techniques; 2) the importance of eating a variety of foods from all food groups, taking in enough calories, and losing weight safely and slowly as recommended and emphasized in the program; 3) and the importance of understanding and monitoring potential symptoms of low blood sugar and low blood pressure. Additionally, study staff and peer specialists delivering the intervention will also periodically (e.g., weekly basis) review participants' food logs, weight logs, self-monitoring tools and provide feedback to Peer GLB participants on whether they are taking in enough nutrients. If there is any question about the cause of an injury or the need for treatment, or if a participant experiences sudden, dramatic weight loss, or signs of low blood sugar or low blood pressure, we will refer them to their physician and stop the intervention as recommended by their physician. The project also has primary care physician, [name], readily available to provide consultation to study staff regarding any potential medical issues.

12. Data and Safety Monitoring

Describe how data and safety will be monitored locally to identify unanticipated problems (i.e., events, outcomes, or occurrences that are unexpected, at least possibly related to the research, and suggest an increase in risk of harm to subjects or others). [name] (PI) and [name] (Project Director) will be responsible for data and safety monitoring. The following steps will be used for data and safety monitoring:

1. At Bi-monthly meetings (twice a month), the PI and Project Director will review rates of enrollment and study retention, any problems with participant safety, and the status of data collection. Protocol violations will be discussed and, if appropriate, the IRBs will be consulted and corrective actions devised.

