2. Although the risks to participants from this protocol are likely to be low (given medically unstable participants are excluded), these risks will be continuously monitored and appropriate measures implemented in cases of unforeseen adverse events, including the removal of participants from the study protocol. For example, if participants became suicidal during the protocol, they would be removed from the study and given appropriate clinical care at the study site.
3. Every 2 months during the intervention phases of the study, the PI and Project Director will review the number of participants enrolled, the number who discontinued participation (and reasons why), the number who did and did not complete study procedures (and reasons why), any adverse events, procedures for assuring participant privacy and confidentiality, and the quality and integrity of the data collected. Corrective action will be taken if needed.

4. IRB protocols and informed consent documents will be reviewed annually by the CU IRB and respective IRBs (e.g., supportive housing agency IRB). Reports of enrollment and retention and reporting of adverse events are required with these renewals. Research Meetings for Data Safety and Monitoring: Throughout the project, frequent research staff meetings will be held with all study personnel to coordinate the study and to assess the progress and status of participants. The PI and Project Director will supervise the day-to-day operations of the study staff. Ad hoc meetings will be performed at Columbia University School of Social Work Offices or study sites with Co-investigators, in order to discuss and resolve any participant-specific issues. These meetings will be attended by the PI, Project Director and study staff. In addition, monthly regular project steering committee with the PI, study staff, representatives from study sites and Co-investigators will be performed to discuss general updates and performance of the project.

Adverse Events: In consultation with the DSMB and pursuant to Human Subjects Regulations and CU IRB protocol, the PI will adhere to the following protocol for adverse events.

- 1) Adverse events may be initially identified by RAs, the Project Director, PI, or other project staff, including staff reviewing audio recordings of Peer GLB sessions, or they may be reported by participants or their providers at the supportive housing agency.

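### As written, early discontinuation removes participants from the study and not only from the intervention, so later primary weights may go uncollected, and the named ascertainer exists only in the Peer GLB arm

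*Combined protocol and SAP*

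**What the plan says.** The rule stands in section 3, Criteria for Early Discontinuation. On who applies it: "Early discontinuation from the study will be ascertained by the group facilitator in consultation with the participants' service providers (e.g., case managers"). On its effect, participants who need detoxification or "are at acute risk of suicide or homicide will be referred for treatment and discontinued from the study". Those who develop a contraindication to a weight loss program are treated alike. The examples are active cancer treatment, liver failure and a cardiovascular event, and the list ends with participants who "become pregnant or are planning a pregnancy during the study period will be discontinued from the study". Section 12, item 2, gives a matching example: "if participants became suicidal during the protocol, they would be removed from the study".

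Elsewhere the protocol uses narrower terms. On missing medical clearance, section 3 says "Failure to obtain this approval letter will preclude the individual from participating in the Peer GLB intervention", and section 7 says the same of a letter not submitted by the first session: it "will preclude the person from participating in the Peer GLB intervention". Section 11, on injury, sudden weight loss, low blood sugar or low blood pressure, says "we will refer them to their physician and stop the intervention as recommended by their physician".

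On the facilitator role, section 3 (Description of Peer Specialists) says "Peer GLB will be facilitated by trained peer-specialists employed at the supportive housing agencies". The recruitment script in section 7 tells clients that those assigned to usual care will not take part in the program.

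The primary hypothesis (section 2) compares the proportions with 5% weight loss at 12 and 18 months. Those weights come from in-person assessments by a research assistant (sections 3 and 5).

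**The concern.** There are two linked problems.

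**Scope.** The stated medical reasons are contraindications to a weight loss program. They justify stopping the program. They do not by themselves justify ending a weighing and an interview. A usual-care participant is not in the program, so applying the rule there removes outcome data without stopping any exposure. Cancer treatment, liver failure and pregnancy can change weight directly, so the missing weights may be related to the outcome. Data never collected cannot be recovered in analysis.

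**Decision-maker.** The rule names a person whom only one arm meets. If facilitators apply it to the participants they see, discontinuation before month 12, and any loss of weights that follows, could be more frequent in Peer GLB than in usual care. Missingness that differs by arm and relates to outcome can bias the primary comparison, and a larger sample would not remove that bias.

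**Working it through.** The available text states no discontinuation rate, response rate, alpha or power, so there is no planned figure to reproduce. The check is mainly textual, with arithmetic for scale.

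**1. Wording compared**

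| Place | Event | What stops |
|---|---|---|
| Section 3, Criteria for Early Discontinuation | Six listed reasons | Study |
| Section 12, item 2 | Becoming suicidal | Study |
| Section 3 (randomization paragraph) and section 7 | No clearance letter | Intervention |
| Section 11 | Injury, rapid weight loss, low blood sugar or pressure | Intervention |

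The authors had intervention-only wording and did not use it in the first two rows. The script in section 7 says interviews will continue whichever group is assigned. That concerns allocation and does not cover discontinued participants.

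**2. Primary time points lost, if the rule is applied literally**

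- Discontinued before month 12: 2 of 2.
- Discontinued between months 12 and 18: 1 of 2.

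**3. Scheduled contact with the named ascertainer over 12 months**

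- Peer GLB, schedule in section 2: 12 weekly + (3 months x 2) + 6 monthly = 24 sessions.
- Peer GLB, script in section 7: 12 + 9 = 21 sessions.
- Usual care: 0.

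These are contacts, not discontinuations. After month 12 there are no scheduled sessions in either arm, so this route to unequal loss applies only before month 12.

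**4. Share of an arm left unobserved**

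With n = 150 per arm (section 1, an upper limit), each lost weight leaves 1/150 = 0.67 points unobserved. If 2, 5 or 10 in an arm are discontinued before month 12 (assumed), the share is 2/150 = 1.3, 5/150 = 3.3 or 10/150 = 6.7 points at both time points.

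**5. Illustrative bias with no true effect**

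Let p be the true response proportion (assumed 20% in both arms), d the proportion lost, and q the proportion of those lost who would have responded. The complete-case proportion is (p - d q)/(1 - d).

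| Loss, Peer GLB vs usual care (assumed) | q (assumed) | Peer GLB | Usual care | Difference |
|---|---|---|---|---|
| 10% vs 2% | 0 | 0.20/0.90 = 22.2% | 0.20/0.98 = 20.4% | +1.8 points |
| 10% vs 2% | 0.5 | 0.15/0.90 = 16.7% | 0.19/0.98 = 19.4% | -2.7 points |
| 15% vs 5% | 0 | 0.20/0.85 = 23.5% | 0.19 + 0.01 = 0.20; 0.20/0.95 = 21.1% | +2.5 points |
| 15% vs 5% | 0.5 | 0.125/0.85 = 14.7% | 0.175/0.95 = 18.4% | -3.7 points |

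The direction depends on what those lost would have done.

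**6. Illustrative power**

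Power is Φ[(Δ - 1.96 SE0)/SE1], where Δ is the difference in proportions, SE0 uses the pooled proportion and SE1 the separate ones. Assume two-sided alpha 0.05 and 15% vs 30% responders. With 150 per arm, SE0 = 0.0482 and SE1 = 0.0474, so power is 87.9%. With 135 and 147 remaining (10% vs 2% loss), it is 85.9%. At 20% vs 35% it falls from 83.2% to 80.9%. The power cost is about 2 points, so bias is the main issue.

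**The case against.** The strongest reply is that study is used loosely here. The medical reasons are contraindications to a program that usual care does not receive, and the named ascertainer exists only in Peer GLB. Both facts fit a rule meant to stop the program, in which case no weight is lost. The protocol nowhere says outright that weighing stops. This stands as far as it goes: a reader might infer that primary weights will certainly be lost, and the documents do not support that. The section 12 example points the other way, however, and staff will apply the words as written.

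A reader might also infer that discontinuation will be higher in Peer GLB and will bias the result in a known direction. The documents do not support that either. The facilitator must consult service providers, who serve both arms. Research assistants ask the self-harm items in both arms. Research staff and providers can report adverse events in either arm. The PI and Project Director review discontinuations and their reasons every 2 months during the intervention phases (section 12, item 3), and the DSMB reviews retention. These limit the asymmetry, but none guarantees continued weighing or names an arm-neutral decision-maker.

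Two further points have force. Some recovered weights, during pregnancy, cancer treatment or liver failure, say little about lifestyle weight loss and need separate handling. Ending an interview for someone at acute suicide risk is a defensible safety choice, so assessments should depend on clinical judgment.

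Part of section 12, the consent pages and the grant mentioned in section 1 were not in the copy reviewed. Follow-up terms there could not be checked.

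**Conclusion.** The concern holds in a conditional form. Under the available text, applying the rule as written would leave remaining 12- and 18-month primary weights uncollected, for reasons that can affect weight. Naming a Peer GLB role as ascertainer leaves open a difference by arm before month 12, which is not demonstrated.

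Its size is unknown, because the documents give no discontinuation rate. The firm figures are 0.67 points of an arm per missing weight (at 150 per arm) and one or two primary time points per discontinued participant. The bias range of +2.5 to -3.7 points across the scenarios rests on assumed losses of up to 15% vs 5%, an assumed 20% response in both arms, and complete-case analysis. It shows scale and is not a forecast. The change should be made because it is cheap and uncollected weights cannot be replaced later. Confidence is medium, since the intended meaning may be narrower than the wording.

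**What to change.** **Section 3, Criteria for Early Discontinuation.** Keep the criteria and treatment referrals, and revise the rule to say:

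- The PI or Project Director, advised by the agency treatment team, decides and records discontinuation by the same criteria in both arms. Facilitators, research assistants and providers report possible cases to them.
- Discontinuation stops the Peer GLB intervention. In usual care the event is recorded and usual services continue.
- Discontinuation does not end follow-up. Remaining 6-, 12- and 18-month assessments, or at least weight, are offered in both arms when the treatment team judges it safe and the participant agrees.
- Weights taken during pregnancy, active cancer treatment or liver failure are flagged for a sensitivity analysis.

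**Section 12, item 2.** Leave the suicidality trigger and the clinical care unchanged. Change only the consequence, to removal from the intervention with remaining assessments offered when the treatment team judges it safe.

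**Cost.** An IRB modification, possibly revised consent wording, a short decision record, and a safety judgment before each visit. The visits are already in the schedule, at about 60 minutes (section 5) and $25 plus transport (section 7). With an assumed 2 to 10 discontinued per arm and at most 3 visits each, that is 2 x 3 = 6 to 10 x 3 = 30 visits, or 6 x $25 = $150 to 30 x $25 = $750 per arm before transport.

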All participants in this study will be asked to participate in four interviews with study staff to learn about your ongoing experiences with your health, weight, physical activity, and quality of life issues. This means that no matter what group you are assigned to, we would like to continue to conduct interviews with you. During these interviews, study staff will 1) measure your weight, height, blood pressure, and waist circumference and 2) ask you questions about various aspects of your life including your health, physical activity, mental health recovery, service use, and quality of life. These interviews will occur just before random assignment, and then every six months after that for 18 months. All interviews will be conducted at [site]. Participation in this project is completely voluntary and all of the information collected for this study will be kept confidential. In order to participate in the study, we first have to ask you some questions to determine if you are eligible. If you are interested in learning whether you are eligible, we would like to schedule a time with you so that we can ask you questions about certain medical or mental health conditions that you may have which may affect whether you are eligible to participate.”

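### Participants with listed clinical events are discontinued from the study, not only the sessions, and nothing says their 6-, 12- and 18-month weights are still taken

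*Combined protocol and SAP*

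**What the plan says.** Two places take participants out of the study.

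- **Section 3, Criteria for Early Discontinuation.** Those needing detoxification or at acute risk of suicide or homicide "will be referred for treatment and discontinued from the study". Those who start cancer treatment, develop liver failure, have a cardiovascular event or "become pregnant or are planning a pregnancy during the study period will be discontinued from the study". The group facilitator ascertains this, in consultation with agency service providers.
- **Section 12, item 2.** Unforeseen adverse events may lead to measures "including the removal of participants from the study protocol". As an example, "if participants became suicidal during the protocol, they would be removed from the study".

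Two places restrict only the intervention, for other reasons.

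- **Section 3, on medical clearance.** "Failure to obtain this approval letter will preclude the individual from participating in the Peer GLB intervention".
- **Section 11.** After an injury, sudden weight loss, or signs of low blood sugar or low blood pressure, staff refer the participant and "stop the intervention as recommended by their physician".

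The nearest statement about continued follow-up is in the section 7 recruitment script: "no matter what group you are assigned to, we would like to continue to conduct interviews with you". It concerns the assigned arm and is silent on people who have been discontinued. Section 3 schedules assessments at 6, 12 and 18 months for clients in general. Section 2 sets the primary outcome as the proportion with 5% weight loss at 12 and 18 months and names example models. It gives no analysis set and no rule for missing weights.

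**The concern.** Cancer treatment, liver failure, a cardiovascular event and pregnancy can each change weight. If people with these events are no longer weighed, the missing values of the primary outcome are related to that outcome, and the comparison is restricted to those who stayed free of a trigger. Earlier weights and recorded reasons for discontinuation help an analyst but do not replace weights at 12 and 18 months that were never taken.

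The wording also leaves site staff to decide what discontinuation means. Usual-care participants attend no sessions. If the rule concerns sessions, it does nothing in their arm; if it concerns the study, it ends their follow-up. Staff at three agencies could apply it differently.

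**Working it through.** **Text.** The protocol has distinct wording for barring or stopping the intervention (sections 3 and 11) and uses different wording for the listed events (sections 3 and 12). That contrast makes loss of follow-up the plain reading. No available statement on assessments overrides it.

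**Scale.** The documents give no event rates, responder rates, dropout rate or power calculation, so there is no planned figure to reproduce. Only the 150 per arm and the visit times come from the protocol (sections 1 and 2). The other inputs are assumptions:

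- e, the fraction of each arm with a medical trigger over 18 months: 2% to 5%. It is kept low because entry criteria exclude people who already have these conditions, and the expected sample is 70% male with an average age near 50.
- pk, responders among those without an event: 20%, varied from 10% to 30%.
- pr, responders among those with an event: 5% to 40%.
- r, the fraction of events removed: 1 in Peer GLB; ru in usual care.
- No true treatment effect, and the same e in both arms.

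Observed rate in an arm = [(1 − e)·pk + e·(1 − r)·pr] / (1 − e·r). With r = 1 in Peer GLB this reduces to pk there, so

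bias (Peer GLB minus usual care) = e·(1 − ru)·(pk − pr) / (1 − e·ru).

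Example: e = 0.05, ru = 0.5, pk = 0.20, pr = 0.05 gives 0.05 × 0.5 × 0.15 / 0.975 = 0.0038, or +0.38 points.

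Bias in percentage points:

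| pk | pr | e = 2%, ru = 0.5 | e = 5%, ru = 0.5 | e = 5%, ru = 0 |
|---|---|---|---|---|
| 20% | 5% | +0.15 | +0.38 | +0.75 |
| 20% | 40% | −0.20 | −0.51 | −1.00 |
| 10% | 5% | +0.05 | +0.13 | +0.25 |
| 10% | 40% | −0.30 | −0.77 | −1.50 |
| 30% | 5% | +0.25 | +0.64 | +1.25 |
| 30% | 40% | −0.10 | −0.26 | −0.50 |

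With ru = 1 (equal removal) the bias is zero throughout. For comparison, the standard error of the difference at 20% responders is √(2 × 0.2 × 0.8 / 150) = 0.046, or 4.6 points.

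**Weights lost**, with all events removed and spread evenly over 18 months:

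- Month 12: 150 × e × 12/18 = 2.0 to 5.0 per arm.
- Month 18: 150 × e = 3.0 to 7.5 per arm.

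**Detectable difference** (assumed 20% usual-care rate, 80% power, two-sided 5%, unpooled normal approximation): d = (1.960 + 0.842)·√{[0.2 × 0.8 + (0.2 + d)(0.8 − d)]/n}. This gives 14.2 points at n = 150, 14.35 at n = 147 and 14.6 at n = 142.5.

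Removals for detoxification need or for suicide or homicide risk would add to the lost weights and are not estimated.

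**The case against.** The strongest reply is that the paragraph is loosely drafted. It presents the medical triggers as reasons why a weight-loss programme is unsuitable and puts the group facilitator in charge, which fits stopping sessions. It also joins its triggers with a conjunction that, taken literally, would require them to occur together, so it is selective to read one word strictly and another loosely. If the study here means the sessions, no weights are lost. This stands as a reason for caution: the text shows an ambiguity whose plain reading is harmful, not proof that weighing stops. It does not remove the need to reconcile the passages.

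Second, the numbers are small and every rate is assumed. That also stands. The largest shift, 1.5 points, is about a third of one standard error.

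Third, some safeguards exist. During the intervention phases, discontinuations and their reasons are reviewed every two months (section 12, item 3), the DSMB monitors retention, and mixed models can use earlier weights. None of these obtains the missing 12- and 18-month weights.

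Fourth, part of section 12 is missing from the available copy, and the grant and consent forms are attachments not seen here. They may address follow-up.

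A reader might go further and infer that triggers will be detected unequally, since the facilitator exists only in Peer GLB and review of session recordings adds a route in that arm. The documents do not support more than a possibility, mainly for the medical triggers. Agency providers, participant and provider adverse-event reports, and BASIS-24 at every assessment reach both arms. If weights are kept for everyone, unequal detection largely stops mattering for the primary outcome.

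**Conclusion.** The point holds as a wording defect with a real consequence on its plain reading: participants with weight-related events leave the study, and no available text keeps their primary-outcome weights. On the assumed rates, about 2 to 5 weights per arm are lost at month 12 and 3 to 8 at month 18. Bias is under 1 point when half of usual-care events are also removed, up to about 1.5 points when none are, and zero under the model when removal is equal. Its actual size and sign cannot be determined from the documents. It would be wrong to conclude that the comparison is materially biased, that detection is shown to differ between arms, or that the protocol certainly stops weighing these participants. The change is still worth making, because it is cheap and a weight not taken cannot be recovered later.

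**What to change.** Leave the clinical triggers and the stopping of sessions as they are. Then:

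1. Reconcile Criteria for Early Discontinuation and the clearance-letter text (section 3), the recruitment script (section 7), Potential Risks (section 11) and item 2 of section 12. Stopping the intervention should be stated separately from ending outcome assessment, and each reference to discontinuation or removal should say which it means.
2. In both arms, continue to invite discontinued participants to the remaining 6-, 12- and 18-month assessments unless they withdraw consent. Any clinical exception is for the investigators to define.
3. Keep these participants in the as-randomised 12- and 18-month comparison, and report discontinuations by arm and reason.

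The cost is an amendment approved by the Columbia IRB and the other site IRBs, plus a few follow-up interviews at $25 and transport each. For the medical triggers at the assumed rates, the interviews per arm are 1 to 2.5 at month 6 (150 × e × 6/18), 2 to 5 at month 12 and 3 to 7.5 at month 18. That is 6 to 15 per arm, or 12 to 30 in total: $300 to $750 plus transport. Removals for the other triggers would add to this.
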